4.1 Study Duration

The study is anticipated to be completed in two years

4.2 Outcome Variables/Endpoints

4.2.1 Primary Outcome Variables/Endpoints

Primary outcome: Group difference in change in question 6 of the CEQ-6 from baseline to after the presentation

4.2.2 Secondary and Exploratory Outcome Variables/Endpoints

Secondary Outcome: Group difference in change in MADRS score from baseline to 24 hours after first treatment

Exploratory outcomes:

Group difference in change in CEQ-6 from baseline to 24 hours after first treatment and after follow-up session

Group difference in change in MADRS score by the end of the acute series of treatments

Group difference in the side effect profile

5 Study Participants

5.1 Study Population

Adult patients with a depressive episode for whom it has been determined by their primary mental health provider that esketamine is an appropriate treatment and have already been deemed appropriate and scheduled for clinical esketamine treatment at Yale Interventional Psychiatry Service according to existing FDA REMS that includes diagnoses of treatment resistant depression, or depression with suicidal ideation, will be eligible for participation in the study.

5.2 Number of Participants

We aim to enroll a total of 34 patients (17 per arm) for this study.

5.3 Eligibility Criteria

Inclusion criteria:

To take part in this study, the following eligibility criteria must be met:

- Participants must be either male or female and at least 18 years old
- Deemed clinically appropriate to receive esketamine by a Yale Interventional Psychiatry physician.

- Written consent for the study procedures
- Ability and willingness, in the investigator's judgement, to comply with the study schedule, treatment plan, and other trial requirements for the duration of the study.

Exclusion criteria:

Any individual who meets any of the following criteria will be excluded from participation in this study:

- Hearing or visual impairment to the degree that would interfere with ability to view the presentation
- Difficulty in understanding spoken or written English
- Unable to provide informed consent
- Dementia or other cognitive disorder or intellectual disability that would impair the subject's ability to understand the presentation (per investigator judgment)
- Any other medical or psychiatric comorbidity that the investigator judges would put the participant at additional undue risk due to study participation or would impair subject's ability to participate in the study.
- Previous Esketamine or ketamine treatment
- Unable to give informed consent
- Was previously enrolled/randomized into the trial

Note: Since only patients who have already been deemed clinically appropriate and are planned to receive esketamine are approached, and participation in the study does not influence patients receiving or not receiving esketamine, exclusions for this medication are not included in the study exclusion criteria.

5.4 Recruitment Procedures

Potential subjects will be referred to the study team by the interventional psychiatry physician who has seen the patient in clinical evaluation for esketamine, after ascertaining their agreement to be approached for the study. At this time, the patient will be reached out by a study team member and informed about the study.

5.5 Consent/Assent Procedures/HIPAA Authorization

- Consent forms describing in detail the study intervention, study procedures, and risks are given to the participant and written documentation of informed consent is required prior to starting procedures/administering study intervention.
- Consent forms will be Institutional Review Board (IRB)-approved and the participant will be asked to read and review the document. The study team member consenting the participant will explain the research study to the participant and answer any questions that may arise. This conversation will take place in a private room.

- Participants will have the opportunity to carefully review the written consent form and ask questions prior to signing. The participants should have the opportunity to discuss the study with their family or surrogates or think about it prior to agreeing to participate.
- Participants must be informed that participation is voluntary and that they may withdraw from the study at any time, without prejudice. A copy of the informed consent document will be given to the participants for their records.
- Note: Given the nature of the study, the consent form will not provide details about the main objectives of the study, but will provide a general outline, explaining that the goal is to assess various ways of presenting relevant information to patients, and various ways of follow up after the first treatment. The true objectives of the study will be explained in detail during the debriefing session after the conclusion of all study procedures for each participant.

6 Study Methods/Procedures

6.1 Study Procedures

Potential subjects will be referred to the study team by the interventional psychiatry physician who has seen the patient in clinical evaluation for esketamine, after ascertaining their agreement to be approached for the study. At this time, the patient will be reached out by a study team member and informed about the study.

Screening / Intake Visit

It is estimated the screening intake will take approximately 2 hours. It will consist of the following procedures and assessments and can be completed in up to 5 days:

- a. Informed Consent: A delegated study team member will discuss risks and benefits of participation and review the study overview with the patient as explained above. The patient will sign the informed consent form prior to any study procedures being performed.
- b. Clinical and Demographic Intake (including medical and psychiatric history, medication history, and current medications)
- c. Montgomery-Asberg Depression Rating Scale (MADRS) and Quick Inventory of Depressive Symptomatology (QIDS-SR16)
- d. CEQ-6 questionnaire regarding upcoming treatment course with esketamine
- e. Review of Inclusion/Exclusion Criteria by investigator

Presentation Visit (Intervention group only)

The intervention consists of a short virtual (via Zoom or similar technology) presentation provided to the participants, within 72 hours before the first treatment with esketamine. The presentation includes predetermined slides and content (the presenter will cover the same

slides and topics but will avoid a strict script to retain the personalized feeling of the presentation, an aspect believed to be crucial to the non-specific effects. Further, patients are allowed to engage, ask questions etc.) The presentation will remain factual and provide information from peer-reviewed literature. However, it is designed to convey a strong positive message, highlighting the effectiveness of the treatment. Additionally, a mild and temporary known side effect of the treatment (dysgeusia) will be intentionally highlighted to assess the 4th hypothesis.

Treatment visits:

Both groups will receive the usual treatment and care. Immediately before first and second treatments both groups will complete the CEQ-6 questionnaire. Additionally, the intervention group will complete the presentation feedback form prior to the first treatment. The rest of the treatments (i.e. treatments 3 to 8) will be done without any assessments.

Follow-up visit:

Twenty-four hours after the first treatment, CEQ-6, MADRS, QIDS, side effects, and adverse effects will be collected. Additionally, patients in the intervention group will receive a follow-up session after their first esketamine treatment. The follow up session will utilize one of two versions: “early-responder” content will be presented to patients with a noticeable improvement after first treatment, providing encouragement. “Early non-responder” content will be presented to patients with no noticeable improvement after first treatment, providing reassurance.

End of study visit:

During the end of study visit, MADRS, QIDS and side effects information will be collected. Additionally, a debriefing session will be held, immediately after the last set of assessments are completed. During this session participants will be informed about the nature of the study in detail, including the hypothesized effects of non-specific factors on overall treatment efficacy, and [for participants in intervention group] the intentional emphasis of a minor side effect (dysgeusia) during the presentation compared to usual care. Participants will be given a chance to ask any questions regarding the study.

Table 1: Visit Schedule Table

Timeline based on ketamine/esketamine treatments	Screening session	Within 72h before treatment 1 (intervention group only)	Immediately before Treatment 1	24hr post dose 1	Immediately before Treatment 2	Within 72 hours after 8th treatment
Day (subject to clinical treatment schedule)	-16±14	-3	0	1	5±3	30±3
Interventions						
Presentation		X				
Follow up session				X		
End of Treatment Debriefing						X
Assessments						
Demographics	X					
MADRS	X			X		X
QIDS	X			X		X
Presentation quality feedback*			X			
Side effects*				X		X
Expectations**	X		X	X	X	

6.1.1 Data Collection

Data collection for the study will be conducted in several stages. Firstly, the eligible participants will be approached and consented to participate in the study. A delegated study team member will discuss risks and benefits of participation and review the study overview with the patient as explained above. The patient will sign the informed consent form prior to any study procedures being performed. After that a trained research study team member will collect clinical and demographic information (including medical and psychiatric history, medication history, and current medications) using a custom questionnaire. After that symptom severity will be assessed by a trained and blinded assessor using a Clinician Rated Outcome questionnaire (MADRS) and a Patient Rated Outcome questionnaire (QIDS-SR16). Then participant expectations regarding upcoming treatment course with esketamine will be accessed using the Treatment Credibility and Expectancy Scale (CEQ-6) questionnaire. After this visit the investigator will review the Inclusion and Exclusion Criteria. If the participant is eligible, randomization will take place.

After randomization and within 72 hours before first treatment, participants in the intervention group will receive a virtual presentation on the benefits and potential side effects of esketamine. The presentation will be factual, however it will emphasize the effectiveness of the treatment, and provide notable encouragement and reassurance. The actual treatments will be provided as usual with no change or alteration in dosing, course or other aspects of the treatment.

Participants in intervention group will provide feedback regarding the presentation using a custom form before treatment 1. (See appendix 1)

Twenty-four hours after the first treatment, participants' expectations will be assessed by Treatment Credibility and Expectancy Scale (CEQ-6).

Symptom severity will be assessed by a trained and blinded assessor using a Clinician Rated Outcome questionnaire (MADRS) and a Patient Rated Outcome questionnaire (QIDS-SR16).

Side effects will be assessed by a custom questionnaire based on the side effects reported on the prescription label for esketamine. (See appendix 2)

All data collected will be stored and managed securely and will be regularly monitored to ensure its quality and accuracy.

6.2 Method of Assignment/Randomization

The randomization process in the study will occur after the screening visit and once the eligibility criteria have been checked and it has been determined by the PI that the subject qualifies. The eligible patients will be randomly assigned to either the intervention group or the TAU group with a 1:1 ratio. Randomization will be conducted using the sequentially numbered, opaque sealed envelopes (SNOSE)¹².

6.3 Adverse Events Definition and Reporting

Study investigators will be able to remove patients from the trial based on their clinical discretion and specific patient outcomes. Any adverse events, including grading of severity and attribution to research will be reported.

In this study, AEs will be defined as any event associated with virtual presentation and follow-up sessions whether or not considered intervention related. This includes any physical, psychological or emotional harm, or any other unintended effects experienced by the participant. Adverse events will be considered from the time of consent and will be monitored and recorded throughout the study. AEs evaluation will be done 24 hours after the first treatment and within 72 hours after 8th treatment. Participants will be asked to report any AEs they experience, either spontaneously or during the study visits. AEs will be recorded on the appropriate CRF. Patients will be closely monitored for adverse events.

The following adverse events will be collected from the time of randomization for the study:

- Adverse events that are not listed in the current labeling for esketamine. This includes events that are similar to those on the labeling but differ from the event because of greater severity or specificity.
- Study Treatment Discontinuation Adverse Events
- Events that lead to the discontinuation of esketamine will be collected for the study. These events will be recorded on either an AE or an SAE form.

The study team will document the AEs, its severity, relationship to the intervention, and the actions taken to address it.

An adverse event (AE) or suspected adverse reaction is considered "serious" if, in the view of either the investigator or sponsor, it results in any of the following outcomes: death, a life-threatening adverse event, inpatient hospitalization or prolongation of existing hospitalization, a persistent or significant incapacity or substantial disruption of the ability to conduct normal life functions, or a congenital anomaly/birth defect.

Note: In addition to AEs as described above, a separate side effect form will be collected during the trial which will solely focus on known side effects of esketamine as per the current labeling (See appendix 2).

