Patients who are deemed clinically appropriate for esketamine will be approached for participation in the study. The eligible and consented participants will be randomized at a 1:1 ratio into “intervention” and TAU groups, with the intervention group being presented with the presentation prior to the first treatment, and to receive a “follow up” session within 24 hours after the first treatment. Both groups will otherwise receive treatment as usual during the course. Assessments including treatment expectations and depression severity will be done at baseline, within 24 hours after treatments 1, 2 and 8.

Study Duration

2 years

Outcome Variables

Primary outcome: Group difference in change in question 6 of the CEQ-6 from baseline to after the presentation

Secondary Outcome: Group difference in change in MADRS score from baseline to 24 hours after first treatment

Exploratory outcomes:

Group difference in change in CEQ-6 from baseline to 24 hours after first treatment and after follow-up session

Group difference in change in MADRS score by the end of the acute series of treatments

Group difference in the side effect profile

Locations/Facilities

Yale Psychiatry hospital (YPH) Interventional Psychiatry Services (IPS) unit

Abbreviations

Abbreviation	Explanation
AE	Adverse Events
CMP	Clinical monitoring plan
CEQ-6	Credibility and Expectancy Scale
CRF	Case report form
DCC	Data coordination center
DHHS	Department of Health and Human Services
DSMB	Data Safety Monitoring Board
DRE	Department of Health and Human Services
EC	Ethics Committee
eCRF	Electronic Case Report Forms
GCP	Good clinical practice
HIPAA	Health Insurance Portability and Accountability Act
MADRS	Montgomery-Asberg Depression Rating Scale
NCT	National Clinical Trial
NIH	National Institutes of Health
PI	Principal Investigator

QA	Quality Assurance
QC	Quality Control
QIDS-SR	Quick Inventory of Depressive Symptomatology
SAE	Serious Adverse Event
SAP	Statistical Analysis Plan
SMC	Safety Monitoring Committee
SOP	Standard Operating Procedure
TAU	Treatment as usual
UP	Unanticipated Problem
YCCI	Yale center for clinical investigation

Glossary of Terms

Glossary	Explanation
Adverse Event	Any event associated with esketamine treatment or the virtual presentation and follow-up sessions whether or not considered therapy related.
Dysgeusia	Altered taste

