6.4 Reaction Management

Reaction management refers to the actions taken to manage any adverse events (AEs) that occur during the study. In the event that a participant experiences an AE, the study team will take appropriate measures to manage the reaction, minimize harm, and ensure the safety and well-being of the participant.

The first step in reaction management is to identify and document the AE. Participants will be asked to report any AEs they experience, either spontaneously or during the study visits.

The study team will document the AE, its severity, relationship to the intervention, and the actions taken to address it.

Based on the severity of the AE, the study team may take various actions to manage the reaction. For minor AEs, such as mild nausea or headache, the study team may provide advice or over-the-counter medications to alleviate the symptoms. For more serious AEs, such as hospitalization, the study team will take immediate action to ensure the safety and well-being of the participant.

If necessary, the study team may discontinue the intervention for a participant experiencing a serious adverse event. Participants who experience a serious adverse event will be referred to their treating physician or a specialist for further evaluation and management.

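### Section 6.3 ties adverse events to sessions that only the intervention arm receives, which conflicts with the glossary and with its own collection list and risks unequal recording by arm

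*Combined protocol and SAP*

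**What the plan says.** The Glossary of Terms defines an adverse event (AE) as "Any event associated with esketamine treatment or the virtual presentation and follow-up sessions whether or not considered therapy related". Section 6.3 gives a different rule for this study: "AEs will be defined as any event associated with virtual presentation and follow-up sessions whether or not considered intervention related". Only the intervention arm has these sessions. Section 6.1 titles the first "Presentation Visit (Intervention group only" and says of the second that "patients in the intervention group will receive a follow-up session after their first esketamine treatment".

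On the start of recording, 6.3 first says "Adverse events will be considered from the time of consent and will be monitored and recorded throughout the study". It then introduces a list with "The following adverse events will be collected from the time of randomization for the study". The first item on that list is "Adverse events that are not listed in the current labeling for esketamine", extended to events that resemble labelled ones but are more severe or more specific. The list also takes in events that lead to esketamine being stopped. A note at the end of 6.3 describes a separate form (Appendix 2) for known labelled side effects, collected in addition to AEs. Section 6.4 gives its examples of minor events in the words "For minor AEs, such as mild nausea or headache".

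**The concern.** An AE rule in a randomised comparison should ask the same question of both arms. The defining sentence in 6.3 ties the event to an exposure that exists in one arm only. Staff who apply it record events in the intervention arm and have no basis for recording them in TAU. Staff who apply the glossary or the list record events in both arms. The documents do not say which rule governs.

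This matters because section 2.2 names the main risk as a change in effectiveness and side effects, with the intervention group possibly differing from TAU. AE counts cannot inform that question if the rule for what counts differs by arm, and adding a TAU column to a table later cannot recover events that were never recorded. The written rule also carries more weight than usual here. Section 7.6 provides no external monitoring, section 8.7 leaves safety review to the principal investigator at least annually, and neither Table 1 nor the end-of-study visit in 6.1 lists AEs, although 6.3 calls for an AE evaluation at that time.

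**Working it through.** No figure in the plan is affected and no arithmetic applies, so the check sets the rules side by side.

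**Definitions.** The glossary names two anchors, esketamine and the sessions. Section 6.3 names only the sessions. TAU has the esketamine anchor but not the session anchor, so a TAU event can meet the glossary definition and cannot meet the 6.3 definition.

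**Four events in a TAU participant, under each rule:**

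| Event | Glossary | 6.3 definition | 6.3 list | Appendix 2 |
|---|---|---|---|---|
| Unlabelled event, esketamine continues | Yes, if associated with esketamine | No | Yes | No |
| Labelled effect, esketamine stopped | Yes | No | Yes | Graded, if an item |
| Labelled effect within the label, not serious, esketamine continues | Yes | No | No | Graded, if an item |
| Labelled effect within the label, hospitalised, esketamine continues | Yes | No | No | Graded, if an item |

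The first two rows show that 6.3 contradicts itself: its list collects what its definition excludes. The third row is acceptable if it is intended, since Appendix 2 captures such effects. The fourth row is the gap. Appendix 2 offers None, Mild, Moderate or Severe for each item, with no field for hospitalisation, date or attribution, so the form would not show that the event was serious.

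**Seriousness.** Section 6.3 applies the serious criteria to an AE or a suspected adverse reaction. The fourth event can therefore be classed as serious, but no rule in 6.3 clearly says that it must be collected.

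**Start point.** Section 6.2 places randomisation after screening and the eligibility check. Section 6.1 allows up to 5 days for screening, which includes consent. The two start points thus differ by the time from consent to randomisation, which the documents do not fix.

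**Examples in 6.4.** Nausea and headache are both Appendix 2 items, yet 6.4 treats mild forms of them as AEs. Section 6.3 does not bar a listed symptom from the AE form, so this is an ambiguity about which form to use, not a direct contradiction.

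**The case against.** The strongest reply is that the procedures are the same in both arms. Section 4 says assessments are identical apart from stated exceptions, and the only one then described is the presentation feedback form. Section 6.1 collects adverse effects at 24 hours without an arm limit. Section 6.3 sets its two AE evaluations and its list for everyone, and adds that bodily, mental, emotional or other unintended effects are included. All of this stands, and it rules out three stronger readings that a reader might infer.

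- *The TAU count must be zero, or an intervention-arm excess is built in.* That follows only if one sentence is applied literally and alone. The list in the same section reaches TAU events.
- *The trial cannot tell whether its intervention adds harm.* Depression severity is measured in both arms by MADRS, with a blinded assessor, and by QIDS. Side effects are graded in both arms on Appendix 2, and their group difference is an exploratory outcome. None of these uses the AE definition.
- *Serious TAU events in general go unrecorded.* The serious criteria also cover suspected adverse reactions, and the list takes unlabelled events from either arm. A hospitalisation for worsening depression may fall under the list; whether the label mentions worsening cannot be checked from these documents.

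The start-point conflict does not bias the arm comparison either, since events before randomisation arise without regard to arm.

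The reply does not remove the conflict itself. The added sentence on kinds of harm widens what the event may be but not what it must be associated with. The items on the list are themselves called adverse events, so a reader may take the definition to govern them too.

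**Conclusion.** The point holds as a conflict between stated rules that carries a risk of unequal AE recording. Read literally, the 6.3 definition leaves out every event in 17 of 34 planned participants; under the rest of 6.3 many of those events would be collected. How far recording would differ in practice depends on which rule staff follow, and the documents give no basis for a number. The gap for a TAU hospitalisation within the label, with esketamine continued, remains even when the list is followed.

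This should be corrected because it concerns safety recording and is cheap to repair. It does not threaten the primary CEQ-6 outcome, the MADRS outcomes or the Appendix 2 comparison. The conclusion rests on the wording alone and assumes no unseen case report form instruction that already settles the matter.

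**What to change.** Reconcile the glossary and 6.3 as follows:

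- Use one AE definition that applies identically in both arms and does not depend on having had a session. Record relation to the sessions and relation to esketamine as attributes of each event.
- State one start point.
- Record every event that meets the seriousness criteria, in both arms, whatever its labelling or attribution.
- Keep the present collection of labelled-type events that are more severe or more specific than the label, and of events that lead to esketamine being stopped. Leave other non-serious labelled effects to Appendix 2. Moving all non-serious labelled effects to Appendix 2 would lose AE information that 6.3 now captures.
- Align the examples in 6.4 with this split between forms.

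The cost is a protocol wording change, which needs an approved IRB amendment under section 9.1, and a matching case report form instruction. The downside is some additional AE entries; the documents do not allow their number to be estimated. The sample size, the visits and the treatment do not change.

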2.2 Risks

Intervention-specific Risks

The main risk to participants in the current study consists of a change in the level of effectiveness and side effects from treatment as a result of the study intervention. Specifically, the “intervention” group may experience a different rate of response, or notice side effects to a different degree than the “treatment as usual” group.

Although non-specific effects in general are believed to be responsible for a significant portion of the treatment’s effects, as the current study only targets a small subcategory of non-specific factors, the magnitude of increased risk will be limited. Furthermore, the study is designed to create a difference between groups mainly by potentially improving the outcomes of the “intervention” group.

The “intervention” group may also experience more dysgeusia which is one of the mild and temporary side effects of esketamine, as a result of intentionally highlighting it in the presentation.

Additionally, the “intervention” group may experience some distress during the “post-treatment” session, particularly if they need to review and discuss distressing or uncomfortable experiences from the treatment.

Psychiatric Assessment and Symptom Rating

Discussing symptoms or past experiences can sometimes be stressful. All included evaluations are non-invasive and have been used without difficulty or adverse events in previous studies and clinical practice.

In order to minimize risks associated with the psychiatric ratings and ensure the accuracy of reporting, these measures will be administered by trained research staff. Participants will be informed that they do not need to answer any question on the rating scales or questionnaires that make them feel uncomfortable. Participants will also be informed they can take a break if they become tired from any of the questions or ratings.

Confidentiality

Loss of confidentiality is another potential hazard of any research protocol. The investigators follow a system of specific precautions to ensure the confidentiality of data in this protocol.

Private identifiable information will be collected (name, date of birth, age, telephone number, address, medical and psychiatric history, diagnoses, laboratory tests, and psychiatric rating scores) but will be kept confidential and will not be divulged in any publication emanating from this work. Please see section 8.1, for the protections in place to mitigate confidentiality risks.

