The intervention consists of a short presentation provided to the participants within 72 hours prior to the first treatment of the acute course (see study course below). Both groups will receive the information considered necessary for informed consent for esketamine treatment as part of usual clinical care. The presentation will be in addition to this process. The presentation will be factual, however it will emphasize the effectiveness of the treatment, and provide notable encouragement and reassurance. The actual treatments will be provided as usual with no change or alteration in dosing, course or other aspects of the treatment.

The intervention group will additionally receive a follow up session within 24 hours after the first treatment to provide encouragement and reassurance. There are two different versions for the follow up session, with each participant receiving one of the versions depending on whether they have noticed any improvements since the first treatment. The contents of these sessions will remain factual, but with differing emphasis on encouragement and reassurance depending on participants’ experience with the first treatment.

Study course

Participants in the intervention group will receive the presentation within 48 hours before the first treatment of the acute course of esketamine. They will also receive the follow up session within 24 hours after the first treatment, immediately after assessments are completed.

Assessments will be done at baseline, within 24 hours after treatments 1, 2 and 8, as detailed in Table 1. Assessments will be identical for both groups, with the exceptions described below.

Assessments

Intervention group specific assessments:

Participants will provide feedback regarding the presentation using a custom form (Appendix 1) before treatment 1 and at the end of treatment visit.

Assessments received by both groups:

Participants’ expectations will be assessed by Treatment Credibility and Expectancy Scale (CEQ-6).

[figure not shown]
Symptom severity will be assessed by a blinded assessor using a Clinician Rated Outcome questionnaire (MADRS) and a Patient Rated Outcome questionnaire (QIDS-SR16).

[figure not shown]
Side effects will be assessed by a custom questionnaire (Appendix 2) based on the side effects reported on the prescription label for esketamine.

End of treatment debriefing session:

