A debriefing session will be held at the end of the study at the 1-month follow up visit, immediately after the last set of assessments are completed. During this session participants will be informed about the nature of the study in detail, including the hypothesized effects of non-specific factors on overall treatment efficacy, and [for participants in intervention group] the intentional emphasis of a minor side effect (dysgeusia) during the presentation compared to usual care. Participants will be given a chance to ask any questions regarding the study.

Study Flow Diagram

Prescreen

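### No adverse-event evaluation is scheduled between the follow-up session and Day 30±3, although distress in that session is a named risk of the intervention

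*Combined protocol and SAP*

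**What the plan says.** Section 2.2 lists, among the risks specific to the intervention, that participants in that arm may be distressed in the session after the first treatment, "particularly if they need to review and discuss distressing or uncomfortable experiences from the treatment". Section 6.3 ties its definition of an adverse event to the presentation and the follow-up sessions and includes psychological and emotional harm, so this distress falls within it.

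On timing, section 6.3 says: "AEs evaluation will be done 24 hours after the first treatment and within 72 hours after 8th treatment". Section 6.1 describes the first of these visits: "Twenty-four hours after the first treatment, CEQ-6, MADRS, QIDS, side effects, and adverse effects will be collected". Section 4 (Study course) places the session: "They will also receive the follow up session within 24 hours after the first treatment, immediately after assessments are completed".

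Between the two evaluations, section 6.1 provides one study contact: "Immediately before first and second treatments both groups will complete the CEQ-6 questionnaire". After that, "The rest of the treatments (i.e. treatments 3 to 8) will be done without any assessments". Table 1 agrees: only the expectations row is marked before treatment 2 (Day 5±3). Table 1 has no adverse-event row, and its side-effects row is marked at Day 1 and Day 30±3 only.

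Sections 6.3 and 6.4 also say in general terms that participants are asked to report events, unprompted or at visits. Section 6.3 adds that events are monitored throughout the study.

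At the end of the study, section 4 holds the debriefing "immediately after the last set of assessments are completed".

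**The concern.** The risk in section 2.2 arises in the session itself. If events are asked about before the session and next at about one month, neither scheduled evaluation is well placed to detect it. Section 7.2.1 will describe safety and tolerability by event rates in the intervention group. A low rate of session-related distress could then partly reflect when the question was put. There is also a plain safety interest in a timely question: section 5.1 admits patients with depression and suicidal ideation, section 7.6 provides no external monitoring, and section 8.7 requires safety review only at least once a year.

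The same ordering appears at the end. The debriefing discloses the withheld purpose and the deliberate emphasis on dysgeusia, and no scheduled question follows it.

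**Working it through.** The plan states no figure for this interval. The check is day arithmetic on Table 1 and a comparison of sections.

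**Inputs (Table 1).** Follow-up session: Day 1. Visit before treatment 2: Day 5±3, that is Day 2 to 8. Visit after treatment 8: Day 30±3, that is Day 27 to 33.

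**Gap as scheduled** = day of next evaluation − day of session.
- Shortest: 27 − 1 = 26 days.
- Nominal: 30 − 1 = 29 days, or 29/7 = 4.1 weeks.
- Longest: 33 − 1 = 32 days.

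**Gap if events are asked about before treatment 2.**
- Shortest: 2 − 1 = 1 day.
- Nominal: 5 − 1 = 4 days.
- Longest: 8 − 1 = 7 days.

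**Number exposed.** All 17 participants planned for the intervention arm are due to receive the session.

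**Order on Day 1.** Section 6.1 collects adverse effects in the same list as the CEQ-6, MADRS and QIDS. Section 4 gives the session once assessments are complete. Together these put the adverse-event question before the session. This is an inference: section 4 does not name adverse events among its assessments, and section 6.1 gives no order.

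**Could another item fill the gap?**
- The side-effect form does not. Section 6.3 limits it to labelled effects of esketamine, Appendix 2 has no item about the session, and it is given at the same two time points.
- An assessment after treatment 2 might, since section 4 says: "Assessments will be done at baseline, within 24 hours after treatments 1, 2 and 8, as detailed in Table 1". The synopsis says the same. But Table 1 and section 6.1 schedule nothing after treatment 2 until the end-of-study visit, so the sentence cannot be relied on.

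**Is the second evaluation itself secure?** Section 6.3 requires it. The end-of-study text in section 6.1 lists MADRS, QIDS and side effects but not adverse events, and Table 1 has no row for them.

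**The case against.** A reader might infer that nobody asks about adverse events for four weeks, or that volunteered reports are all that remain. The documents do not support that. Directly after the sentence that sets the two evaluations, section 6.3 has participants asked to report events at study visits as well as unprompted, and section 6.4 repeats it. A visit exists at Day 5±3. Section 6.3 also promises close monitoring, and patients remain in usual clinical care. This objection stands against any claim that distress would go unasked. It does not close the gap in the schedule: the general statement assigns nobody to ask at the Day 5±3 visit, and staff working from section 6.1 and Table 1 would give the CEQ-6 only.

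A reader might also take it as stated that the first evaluation is over before the session begins. It is the natural reading, but no sentence says so.

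Nor do the documents show that a reaction to the debriefing would go without follow-up. Section 6.5 covers events unresolved at the end of the study, and that wording can include one arising in the debriefing. What is missing is a scheduled question afterwards, not the follow-up.

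Finally, the named harm is some distress in a session meant to encourage and reassure, in a study that section 7.6 describes as minimal risk, and no hypothesis tests it. That is a fair argument for treating the point as minor.

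**Conclusion.** The point holds in a limited form. No scheduled adverse-event evaluation falls between the follow-up session and Day 30±3, a gap of 26 to 32 days. Over that time, capture depends on volunteered reports and on a general instruction that the visit schedule does not carry through. It goes beyond wording, because the schedule followed as written most naturally takes the Day 1 evaluation before the exposure it should cover.

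This rests on three assumptions: that adverse events are collected with the other 24-hour assessments, that the session takes place on Day 1 as in Table 1 (whose days are subject to the clinical schedule), and that the notes to the asterisks in Table 1, which are absent from the text available, add no adverse-event item.

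Severity is minor. Safety capture and the rates in section 7.2.1 are affected; the CEQ-6 and MADRS comparisons are not.

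**What to change.** 1. In sections 6.1 and 6.3, have the person giving the follow-up session ask about and record any distress as it closes.
2. Add an adverse-event row to Table 1, with a question in both arms at the existing visit before treatment 2. Ask it after the CEQ-6, so that it cannot influence that rating, and have it asked by staff other than the blinded MADRS assessor, since an answer about the session would reveal the arm.
3. Place the end-of-study adverse-event question after the debriefing, and list adverse events in the end-of-study text of section 6.1 and in Table 1, as section 6.3 already requires. The follow-up in section 6.5 can stay as it is.
4. Reconcile the statement in the synopsis and section 4 about assessments after treatment 2 with Table 1.

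The cost is a few minutes at contacts that already take place and a protocol amendment. No new visit is needed, and no outcome or treatment changes.
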